## **5.6 Premature Termination or Suspension of Study**

This study may be suspended or prematurely terminated if there is sufficient reasonable cause. Written notification, documenting the reason for study suspension or termination, will be provided by the suspending or terminating party to NIDCR and regulatory authorities. If the study is prematurely terminated or suspended, the principal investigator will promptly inform the IRB and will provide the reason(s) for the termination or suspension.

Circumstances that may warrant termination include, but are not limited to:

- Determination of unexpected, significant, or unacceptable risk to subjects
- Insufficient adherence to protocol requirements
- Data that are not sufficiently complete and/or evaluable
- Determination of futility

# **6 STUDY INTERVENTION**

## **6.1 Study Product Description**

Cetuximab (Erbitux®) is a Monoclonal Antibody/Epidermal Growth Factor Receptor (EGFR) Inhibitor. It is indicated for the treatment of:

- locally or regionally advanced squamous cell carcinoma of the head and neck (SCCHN) in combination with radiation therapy;
- recurrent locoregional disease or metastatic squamous cell carcinoma of the head and neck in combination with platinum-based therapy with 5-FU; and
- recurrent or metastatic squamous cell carcinoma of the head and neck progressing after platinum-based therapy.

See Package Insert for further information.

### **6.1.1 *Acquisition***

Commercial Cetuximab will be utilized in this study. Cetuximab will be prepared and administered per UWHC pharmacy and hospital guidelines.

See Package Insert for further information.

### **6.1.2 *Formulation, Packaging, and Labeling***

Erbitux is a sterile, clear, colorless liquid of pH 7.0 to 7.4, which may contain a small amount of easily visible, white, amorphous cetuximab particulates.

Erbitux is supplied at a concentration of 2 mg/mL in either 100 mg (50 mL) or 200 mg (100 mL), single-use vials. Cetuximab is formulated in a solution with no preservatives, which contains 8.48 mg/mL sodium chloride, 1.88 mg/mL sodium phosphate dibasic heptahydrate, 0.41 mg/mL sodium phosphate monobasic monohydrate, and Water for Injection, USP.

Cetuximab is supplied at a concentration of 2 mg/mL as a 100 mg/50 mL, single-use vial or as a 200 mg/100 mL, single-use vial as a sterile, injectable liquid containing no preservatives.

Cetuximab can be supplied to two dosage forms:

- A 100 mg/50 mL, single-use vial, individually packaged in a carton (NDC 66733-948-23)
- A 200 mg/100 mL, single-use vial, individually packaged in a carton (NDC 66733-958-23)

### **6.1.3 *Product Storage and Stability***

Product vials will be stored under refrigeration at 2° C to 8° C (36° F to 46° F). Product will not be frozen. Increased particulate formation may occur at temperatures at or below 0° C. This product contains no preservatives.

Preparations of Erbitux in infusion containers are chemically and physically stable for up to 12 hours at 2° C to 8° C (36° F to 46° F) and up to 8 hours at controlled room temperature (20° C to 25° C; 68° F to 77° F). Any remaining solution will be discarded in the infusion container after 8 hours at controlled room temperature or after 12 hours at 2° to 8° C. Any unused portion of the vial will be discarded.

## **6.2 *Dosage, Preparation and Administration of Study Product***

### ***Cetuximab Preparation***

Cetuximab will not be administered as an intravenous push or bolus. It will only be administered via infusion pump or syringe pump. The infusion rate will not exceed 10 mg/min.

Cetuximab will be administered through a low protein binding 0.22-micrometer in-line filter.

Parenteral drug products will be inspected visually for particulate matter and discoloration prior to administration, whenever solution and container permit. The solution should be clear and colorless and may contain a small amount of easily visible, white, amorphous, cetuximab particulates. The solution is not to be shaken or diluted.

### **Cetuximab Administration Guidelines**

Treatment with cetuximab will occur during the period between initial diagnosis and surgical resection. The standard of care (SOC) commonly utilizes approximately 4 weeks after diagnosis for preoperative scheduling and medical optimization. As such, this clinical trial does not delay standard of care curative treatment for head and neck cancer.

Prior to administration of cetuximab, subjects will be premedicated with diphenhydramine and acetaminophen as described in Section 6.6.

For Dose #1, subjects will be treated with cetuximab  $400 \text{ mg/m}^2$  via intravenous infusion over 2 hours (maximum infusion rate 10 mg/min) as per the standard of care loading regimen for cetuximab monotherapy.

For Dose #2, subjects will be treated with cetuximab  $250 \text{ mg/m}^2$  via intravenous infusion over 1 hour (maximum infusion rate 10 mg/min) as per the standard of care dosing regimen for cetuximab monotherapy.

See section 6.6 for concomitant medication as cetuximab pretreatment.

### **Cetuximab Administration Monitoring**

- Vitals signs will be monitored every 15 minutes for the first hour, and then every 30 minutes until cetuximab infusion is complete for the first infusion as per the University of Wisconsin Hospital and Clinic guidelines. The nurse should remain with the patient for the first 15 minutes of drug administration for the first and second dose of cetuximab administration as per the University of Wisconsin Hospital and Clinics guidelines
- Hypersensitivity reaction to cetuximab can occur. For first and second dose, patient should be treated in a location to optimize emergency care.
- For the first dose of cetuximab, the subject must remain in the treatment area for 60 minutes following the completion of the cetuximab as per the University of Wisconsin Hospital and Clinics guidelines.

### **Supportive Care**

Optimal patient care is to be given to all patients.

### **6.2.1 Potential adverse events and precautions**

#### *Infusion Reactions*

Serious infusion reactions can occur during cetuximab administration. Serious infusion reactions include rapid onset of airway obstruction (bronchospasm, stridor, hoarseness), hypotension, shock, loss of consciousness, myocardial infarction, and/or cardiac arrest. Severe (NCI CTC Grades 3 and 4) infusion reactions occurred in 2–5% of patients in prior clinical studies with a fatal outcome in 1 patient [Cetuximab FDA prescribing information].

Approximately 90% of severe infusion reactions occurred with the first infusion despite premedication with antihistamines. Thus, patients must be monitored for at least 1 hour following cetuximab infusions in a setting with resuscitation equipment and other agents necessary to treat anaphylaxis (e.g., epinephrine, corticosteroids, intravenous antihistamines, bronchodilators, and oxygen). For any subjects who experience an infusion reaction, longer monitoring may be necessary and is appropriate to confirm resolution of the event.

In the event of an infusion reaction,

- For NCI CTC grade 1, grade 2, and non-serious grade 3 infusion reaction, cetuximab will be temporarily held with administration of emergency medications as appropriate by the treating physician. Upon resolution of the infusion reaction, subjects may be rechallenged with cetuximab at a reduced infusion rate.
- For serious grade 3 and all grade 4 infusion reactions, cetuximab will be permanently discontinued.
- All subjects should receive appropriate medical intervention as appropriate by the treating physician
- Emergency medications to be available in the event of an infusion reaction include:
  - Diphenhydramine 25-50 mg IV
  - Dexamethasone 4-10 mg IV
  - Albuterol nebulization solution 2.5 mg/3ml

#### *Cardiopulmonary Arrest*

Cardiopulmonary arrest and/or sudden death occurred in 4 (2%) of 208 patients treated with radiation therapy and cetuximab as compared to none of 212 patients treated with radiation therapy alone. Three patients with prior history of coronary artery disease died at home, with myocardial infarction as the presumed cause of death. One of these patients had arrhythmia and one had congestive heart failure. Death occurred 27, 32, and 43 days after the last

dose of cetuximab. One patient with no prior history of coronary artery disease died one day after the last dose of cetuximab. In Study 2, fatal cardiac disorders and/or sudden death occurred in 7 (3%) of 219 patients treated with EU-approved cetuximab and platinum-based therapy with 5-FU as compared to 4 (2%) of 215 patients treated with chemotherapy alone. Five of these 7 patients in the chemotherapy plus cetuximab arm received concomitant cisplatin and 2 patients received concomitant carboplatin. All 4 patients in the chemotherapy-alone arm received cisplatin. Cardiopulmonary arrest and/or sudden death has been observed in a small percentage of patients during the trials that have led to approval of cetuximab, resulting in the issuance of an FDA black box warning.

During cetuximab treatment and after completion of cetuximab treatment, subjects will have close monitoring of serum electrolytes, including serum magnesium, potassium, and calcium.

Development of cardiopulmonary arrest will result in permanent discontinuation of cetuximab.

#### *Pulmonary Toxicity*

Interstitial lung disease (ILD), including 1 fatality, occurred in 4 of 1570 (<0.5%) patients receiving cetuximab in colorectal cancer and head and neck cancer.

- Subjects who develop acute onset pulmonary symptoms should have the cetuximab withheld and be evaluated by the treating physician.
- Subjects who have confirmed interstitial lung disease after treatment with cetuximab will be permanently discontinued from cetuximab treatment.

#### *Dermatologic Toxicity*

Dermatologic toxicities, including acneiform rash, skin drying and fissuring, paronychial inflammation, infectious sequelae (for example, *S. aureus* sepsis, abscess formation, cellulitis, blepharitis, conjunctivitis, keratitis/ulcerative keratitis with decreased visual acuity, cheilitis), and hypertrichosis occurred in patients receiving cetuximab therapy. Acneiform rash occurred in 76–88% of 1373 patients receiving cetuximab. Severe acneiform rash occurred in 1–17% of patients. Acneiform rash usually developed within the first two weeks of therapy and resolved in a majority of the patients after cessation of treatment, although in nearly half, the event continued beyond 28 days.

- Study subjects will be monitored for dermatologic toxicities and infectious sequelae.
- Subjects will be instructed to limit sun exposure during cetuximab treatment
- Severe (NCI CTC Grade 3 or 4) acneiform rash will result in discontinuation of cetuximab therapy.

- Intolerable grade 2 rash, despite maximum supportive care, will result in discontinuation.
- NCI CTC Grade 1 or 2 rash is to be treated with one or more of the following medications at the treating physician's discretion, based upon supportive care evidence. Potential medications that can be used for the treatment of cetuximab-related rash may include, but are not limited to, the following:
  - Hydrocortisone 1 to 2.5% lotion
  - Doxycycline 100 mg bid
  - Clindamycin 1% lotion

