### **6.3 Modification of Study Product Administration for a Subject**

#### **Dose Delays/Dose Modifications**

- No dose modifications will be planned. Please refer to section 6.2.1 (subsection, Infusion Reactions) for more information regarding infusion rate decreases in the setting of infusion reaction.
- Dose delays secondary to intolerance (such as infusion reactions) are permitted. Subjects can be rechallenged with cetuximab within 3 days but will otherwise be discontinued from the study.
- Expected adverse events that would delay cetuximab infusion:
  - Grade 3 or higher nausea, vomiting, diarrhea, stomatitis, or rash uncontrolled despite maximal medical management due to a toxicity that is considered at least PROBABLY related to study treatment
  - Any other Grade 3 or higher non-hematologic toxicity, except grade 3 fatigue lasting >7 days, due to a toxicity that is considered at least PROBABLY related to study treatment
  - Grade 3 or 4 electrolyte abnormalities that are corrected within 48 hours will not be considered a serious adverse event.

---

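### Section 6.3 only delays cetuximab for uncontrolled grade 3 or higher rash, where Section 6.2.1 stops it for severe acneiform rash and even intolerable grade 2 rash; its fatigue exemption also appears inverted.

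*Combined protocol and SAP*

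**What the plan says.** Section 6.2.1, Dermatologic Toxicity, gives two stopping rules. The first is "Severe (NCI CTC Grade 3 or 4) acneiform rash will result in discontinuation of cetuximab therapy". The next bullet stops treatment for a grade 2 rash that remains intolerable with full supportive care, and it is not limited to acneiform rash.

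Section 6.3, Dose Delays/Dose Modifications, has a list headed "Expected adverse events that would delay cetuximab infusion". Its first item is "Grade 3 or higher nausea, vomiting, diarrhea, stomatitis, or rash uncontrolled despite maximal medical management", if at least probably related to treatment. Its second covers all other non-hematologic toxicity of grade 3 or higher with the same attribution, "except grade 3 fatigue lasting >7 days".

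A separate bullet in 6.3 says "Dose delays secondary to intolerance (such as infusion reactions) are permitted", and continues: "Subjects can be rechallenged with cetuximab within 3 days but will otherwise be discontinued from the study". The only pointer from 6.3 back to 6.2.1 concerns slowing the infusion after an infusion reaction.

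Dose 2 is due 7 days after dose 1, plus or minus 3 days (Section 7.2; Appendix A, footnote 2). Section 12.2 requires both full doses and surgical resection for the efficacy evaluation.

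**The concern.** Both sections guide the decision on dose 2, and they give different actions for the same patient. Someone with uncontrolled, probably related grade 3 or 4 acneiform rash after dose 1 is taken off cetuximab by 6.2.1 but is only a candidate for delay under 6.3. The ordering across grades is also wrong: a grade 2 rash can end treatment while an uncontrolled grade 3 rash of another type is only postponed.

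The fatigue wording raises a similar worry. Read literally, the more persistent toxicity is the one that does not hold the dose.

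At stake is whether a patient with severe toxicity receives a second dose of a drug whose pre-operative use is the investigational part of this study (Section 4). Because efficacy evaluability depends on both doses, the rule followed can also decide who enters the primary analysis.

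**Working it through.** The plan has no figure of its own on this point, so the check is a comparison of the rules and a day count for the fatigue exemption.

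**Step 1. The rules side by side**, for an event before dose 2 that is at least probably related:

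| Event | Section 6.2.1 | Section 6.3 |
|---|---|---|
| Grade 2 rash, intolerable on full supportive care | Discontinue | Not listed |
| Acneiform rash, grade 3 or 4, uncontrolled | Discontinue | Delay |
| Other rash, grade 3 or higher, uncontrolled | No rule at this grade | Delay |
| Grade 3 fatigue, 7 days or less | No rule | Delay |
| Grade 3 fatigue, more than 7 days | No rule | Exempt from delay |

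Row 2 is the direct conflict. Rows 1 and 3 show the ordering problem. Rows 4 and 5 show the fatigue problem.

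**Step 2. Does other text resolve the rash conflict?** For infusion reactions the protocol draws the boundary: lower grades and non-serious grade 3 may be rechallenged at a reduced rate, and "For serious grade 3 and all grade 4 infusion reactions, cetuximab will be permanently discontinued". Section 6.3 draws no such line for rash and gives no recovery grade. Section 5.5.1 lets the treating physician change therapy, and Section 9.5 has the principal investigators review probably attributed events weekly. Both are backstops; neither says which rule applies.

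**Step 3. Can the conflict arise in time?** Section 6.2.1 says acneiform rash usually appears in the first two weeks of therapy. With dose 1 as day 0, the dose-2 window is 7 - 3 = day 4 to 7 + 3 = day 10. Onset before dose 2 is therefore possible.

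**Step 4. When can the fatigue exemption be met?** Assume onset on day 0 or later. Section 7 defines day counting for tests and measurements but not for adverse-event duration, so both counts are shown.

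- Elapsed days (decision day - onset day > 7): day 8 needs onset on day 0 (8 - 0 = 8); day 9, onset on day 0 or 1; day 10, onset on days 0 to 2. That is 3 of the 7 permitted days.
- Inclusive days (decision day - onset day + 1 > 7): day 7 needs onset on day 0 (7 - 0 + 1 = 8); day 8, onset on day 0 or 1; day 9, days 0 to 2; day 10, days 0 to 3. That is 4 of the 7 permitted days.

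The exemption is therefore reachable within the window. It can also be reached after a hold: on the elapsed count, grade 3 fatigue with onset on day 0 delays the dose on day 7 and, if it persists, no longer delays it on day 8.

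**Step 5. Size.** The affected rash group is the overlap of four conditions: grade 3 or higher, before dose 2, uncontrolled, and at least probably related. The documents give no rate for this overlap and no rate for grade 3 fatigue, so no count can be derived.

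**The case against.** The strongest reply is that the two sections impose no contradictory duties. Section 6.2.1 is specific and mandatory; 6.3 is general, and its rechallenge wording is permissive. Stopping cetuximab satisfies both, and reading the specific rule over the general one would settle row 2. This stands in part. A reader might infer that the protocol tells clinicians to re-dose patients with severe acneiform rash, and it does not: 6.3 never requires rechallenge. Moreover, the 3-day sentence sits in the bullet on intolerance, where infusion reactions are the example, so applying it to rash is an inference across bullets. What remains is that 6.3 classes the event as a delay, makes no exception for acneiform rash, and does not defer to 6.2.1 on rash.

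It can also be said that few patients would be affected. This stands. A rash must be uncontrolled and yet judged fit for rechallenge within 3 days; otherwise, if the 3-day sentence applies, 6.3 itself removes the patient. Section 6.2.1 says of acneiform rash that it mostly resolved after treatment ended, "although in nearly half, the event continued beyond 28 days".

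A reader might multiply the 1-17% severe acneiform rash rate in 6.2.1 by 36 and take 0.36 to 6.12 patients as the number affected. The documents do not support that. The rate counts any severe acneiform rash, and the studies cited in that paragraph include radiotherapy-combination and colorectal trials. It is not limited to rash before dose 2 of a two-dose course, nor to uncontrolled and probably related cases.

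On fatigue, the fair objection is that no text states the intended direction. That stands too: the wording exempts the longer duration, but that the shorter one was meant is an inference.

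**Conclusion.** The point holds, with limited reach. As written, 6.3 is more lenient than 6.2.1 for a worse rash, and it lets prolonged related grade 3 fatigue escape a delay that shorter fatigue triggers. The first follows directly from the two texts. The second appears inverted as a safety rule, but the documents do not establish it as a drafting slip.

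The practical risk is that a clinician relying on 6.3 alone gives dose 2 to a patient whom 6.2.1 takes off cetuximab, or gives it on schedule during prolonged grade 3 fatigue. For rash, this rests on carrying the 3-day sentence over to the rash item; the stop-versus-delay mismatch does not. The number of patients cannot be computed. A reader might also infer damage to the trial's error rates or power; there is none. The only statistical link is that the rule followed can change whether an individual patient is evaluable for efficacy. The correction should be made because these are stated dosing rules for severe toxicity and it costs very little.

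**What to change.** In Section 6.3:

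- Remove rash from the first delay item and state that rash is managed under 6.2.1.
- Exclude rash from the catch-all item for other grade 3 or higher non-hematologic toxicity, so that it does not return there.
- Delete the fatigue exception as the safe default. If the clinical team confirms that the exemption was meant for the shorter duration, change it to grade 3 fatigue lasting 7 days or less.

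In Section 6.2.1, keep the acneiform rule and add that uncontrolled grade 3 or higher rash of any type also discontinues cetuximab, in line with the grade 2 rule. Merely limiting the 6.3 item to non-acneiform rash would not be enough: uncontrolled grade 3 non-acneiform rash would still only be delayed, while an intolerable grade 2 rash of any type ends treatment.

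The cost is a few words of protocol text, with alpha, power and the target of 36 unchanged. The downside is possibly an occasional extra patient who does not receive dose 2 and so cannot be evaluated for efficacy. Under Section 12.2 that patient stays in the safety evaluation and may be replaced if the principal investigator so decides.

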#### *Hypomagnesemia and Electrolyte Abnormalities*

- Periodic monitoring for hypomagnesemia, hypocalcemia, and hypokalemia will be performed during and after completion of cetuximab. All abnormalities will be noted in the patient's medical record. The treating clinician will determine if the abnormality is clinically significant. Repletion of electrolyte deficits will be performed as per discretion of the treating physician.

#### *Assessment of Research Biopsy Site*

- Assessment of the research biopsy site will be monitored by treating physician until resolution.

### **6.3 Modification of Study Product Administration for a Subject**

#### **Dose Delays/Dose Modifications**

- No dose modifications will be planned. Please refer to section 6.2.1 (subsection, Infusion Reactions) for more information regarding infusion rate decreases in the setting of infusion reaction.
- Dose delays secondary to intolerance (such as infusion reactions) are permitted. Subjects can be rechallenged with cetuximab within 3 days but will otherwise be discontinued from the study.
- Expected adverse events that would delay cetuximab infusion:
  - Grade 3 or higher nausea, vomiting, diarrhea, stomatitis, or rash uncontrolled despite maximal medical management due to a toxicity that is considered at least PROBABLY related to study treatment
  - Any other Grade 3 or higher non-hematologic toxicity, except grade 3 fatigue lasting >7 days, due to a toxicity that is considered at least PROBABLY related to study treatment
  - Grade 3 or 4 electrolyte abnormalities that are corrected within 48 hours will not be considered a serious adverse event.

---

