### **5.5.1 Reasons for Withdrawal**

In addition to discontinuation from therapy related to toxicities as outlined in the Halting Rules of Section 9.5, a subject will also be discontinued from protocol therapy and followed up per protocol under the following circumstances:

- Documented disease progression
- The treating physician thinks a change of therapy would be in the best interest of the subject.
- The subject requests to discontinue protocol therapy, whether due to unacceptable toxicity or for other reasons.
  - If a subject decides to prematurely discontinue protocol therapy (“refuses treatment”), the subject should be asked if he or she may still be contacted for further scheduled study assessments. The outcome of that discussion should be documented in both the medical records and in the electronic case report form (eCRF).
- A female subject becomes pregnant.
- The subject meets an exclusion criterion (either newly developed or not previously recognized) that precludes further study participation.

Subjects will be removed from protocol therapy and the site investigator notified when any of the criteria listed above apply. The reason for discontinuation of protocol therapy will be documented on the eCRF.

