### **5.5.2 Handling of Subject Withdrawals or Subject Discontinuation of Study Intervention**

If a subject decides to withdraw from the study (and not just from protocol therapy) all efforts should be made to complete and report study assessments as thoroughly as possible. The study team should contact the subject or a responsible relative by telephone to establish as completely as possible the reason for the study withdrawal. A complete final evaluation at the time of the subject's study withdrawal should be made with an explanation of why the

subject is withdrawing from the study. If the reason for removal of a subject from the study is an adverse event, it will be recorded on the eCRF.

If a subject is unevaluable for safety and efficacy endpoints (i.e., lacks molecular/correlative studies, and creation of PDXs, subject has not received both cetuximab doses in their entirety and/or has not had surgical resection of the tumor), then the subject will be replaced at the discretion of the principal investigator.

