## **9.2 Time Period and Frequency for Event Assessment and Follow-Up**

Unanticipated problems will be recorded in the data collection system throughout the duration of the study.

All AE's will be recorded from the time of informed consent until 28 days past last dose of study drug or day of surgery, whichever is first. SAE's will be recorded from the time of informed consent through 28 days past last dose of study drug or 28 days post-surgery, whichever is later. Serious adverse events that occur more than 28 days after surgery and have an attribution of possibly, probably, or definitely related to cetuximab (or other research procedures such as biopsy or blood draws) require reporting per table 1.

At each study visit, the investigator will inquire about the occurrence of AE/SAEs since the last visit. Events will be followed for outcome information until resolution or stabilization.

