### **Procedures for Recording and Reporting Serious Adverse Events**

- SAEs will be reported from time of informed consent until 28 days after discontinuation of cetuximab or definitive surgery, whichever is later.
- Any SAEs experienced after this 28-day period will only be reported if the investigator suspects a causal relationship (possibly, probably or definitely related) to the study treatment.
- SAEs will be reported on the SAE Submission Form and entered in SAE tab in OnCore within 1 business day of discovery of the event.
- SAEs include events related and unrelated to the study drug(s).
- SAEs will be recorded in the subject's medical record and on the appropriate study specific eCRF form within OnCore.
- All SAEs, regardless of relation to study drug, will be followed until resolution to ≤ Grade 1 or baseline and/or deemed clinically insignificant and/or until a new anti-cancer treatment starts, whichever occurs first.
- Recurrent episodes, complications, or progression of the initial SAE will be reported as follow-up to the original episode within 24 hours of the investigator receiving the follow-up information.

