### **9.5 *Halting Rules***

During the conduct of this study, subjects with adverse events and serious adverse events that are probably attributed to cetuximab will be evaluated and

analyzed weekly by the principal investigators. If >25% of subjects have serious adverse events that are probably related to pre-operative cetuximab treatment, then enrollment for the study will be suspended for further analysis.

Subsequent review of serious, unexpected, and related AEs will be evaluated by the DSMC, IRB, and the NIDCR. The NIDCR and local regulatory authorities retain the authority to suspend additional enrollment and administration of cetuximab for the entire study, as applicable.

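### The all-biopsied safety set in 12.2 does not fit the re-admission endpoint, 5.5.2 contradicts 12.2 on who is evaluable for safety, and 6.3 takes patients not rechallenged in time off the study instead of off therapy (minor)

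*Combined protocol and SAP*

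**What the plan says.** **Who counts for safety.** Section 3.2.2 defines the secondary endpoint as re-admission for wound or surgical complications attributed to cetuximab in the 28 days after surgery. Section 12.4 presents it as the measure of safety and reports it as a proportion with an exact 95% interval, without naming an analysis set. Section 12.2 puts everyone who had the research biopsy into the safety evaluation. It requires both full doses and resection only for efficacy, correlative and xenograft work. Section 5.5.2 starts its replacement rule with "If a subject is unevaluable for safety and efficacy endpoints", and the conditions it lists include "subject has not received both cetuximab doses in their entirety and/or has not had surgical resection of the tumor". Such a patient may be replaced at the principal investigator's discretion.

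**What happens after a failed rechallenge.** For delays due to intolerance, Section 6.3 says "Subjects can be rechallenged with cetuximab within 3 days but will otherwise be discontinued from the study". Section 5.5.1 uses a different consequence for its own list of stopping reasons: "a subject will also be discontinued from protocol therapy and followed up per protocol under the following circumstances". For toxicity it points elsewhere: "In addition to discontinuation from therapy related to toxicities as outlined in the Halting Rules of Section 9.5". In Section 9.5 the stated consequence of too many related SAEs is "then enrollment for the study will be suspended for further analysis". Section 9.2 says "SAE's will be recorded from the time of informed consent through 28 days past last dose of study drug or 28 days post-surgery", taking the later of the two, and Section 9.4 agrees: "SAEs will be reported from time of informed consent until 28 days after discontinuation of cetuximab or definitive surgery, whichever is later".

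**The concern.** Neither safety rule gives a sensible population for the re-admission rate. Section 12.2 counts biopsied patients who fail Step 2. The end of Section 5.2 foresees such patients and says where their tissue goes. They receive no cetuximab, so they cannot have a complication attributed to it, and they enlarge the denominator without being at risk. Section 5.5.2, read literally, errs the other way: it sets aside patients who received cetuximab, missed all or part of a dose and still had surgery. Those patients are at risk, and some will have missed a dose because of toxicity.

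Section 6.3 raises a separate question about follow-up. The protocol treats leaving the study and leaving therapy as different states (5.5.2 and 7.4 both draw the line). A coordinator who follows 6.3 as written could stop following a patient who did not tolerate the drug and is about to have surgery, although 9.2 and 9.4 require SAE recording for that patient.

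At stake are the meaning and reproducibility of one descriptive rate in a single-arm, open-label study. If its denominator is not fixed beforehand, it may be chosen after the events are known.

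**Working it through.** **Setting the sections side by side**

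- *12.2 against 5.5.2.* A patient who had the biopsy, one dose and surgery is in the safety evaluation under 12.2 and unevaluable for safety under 5.5.2. This is a direct contradiction. The two passages otherwise share the same two-dose and resection condition, so 5.5.2 looks like a miscopied form of 12.2.
- *6.3 against 9.2 and 9.4.* The SAE windows run to the later of 28 days after the last dose and 28 days after surgery, with no exception for a failed rechallenge. Being off the study is incompatible with that.
- *6.3 against 5.5.1.* A failed rechallenge is not on the 5.5.1 list, so this is an inconsistency in how the protocol handles stopping, not a breach of a rule that names these patients.
- *5.5.1 pointing to 9.5.* Section 9.5 holds weekly review of related events by the principal investigators, suspension of enrolment if more than 25% of subjects have probably related SAEs, and authority to suspend cetuximab for the whole study. It has no rule for stopping therapy in one patient. Those rules are in 6.2.1 and 6.3.

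**Effect of the denominator**

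The plan gives no expected re-admission rate or target precision, so it has no figure of its own to reproduce here. The following inputs are assumptions unless marked:

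- 36 completers (the planned number, Section 12.2), 4 of them re-admitted.
- r = 2 further patients who received cetuximab, missed a dose, had surgery and were replaced; 0 to 2 of them re-admitted.
- B biopsied patients in all, 50 or 100. The upper value takes the roughly 100 screened (Section 5) as a ceiling.

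The rate is x/n. The exact 95% limits are the 2.5% point of Beta(x, n - x + 1) and the 97.5% point of Beta(x + 1, n - x).

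| Set | Fewest events | Most events |
|---|---|---|
| Completers (5.5.2 read literally) | 4/36 = 11.1% (3.1-26.1) | same |
| Any cetuximab and surgery | 4/38 = 10.5% (2.9-24.8) | 6/38 = 15.8% (6.0-31.3) |
| All biopsied, B = 50 | 4/50 = 8.0% (2.2-19.2) | 6/50 = 12.0% (4.5-24.3) |
| All biopsied, B = 100 | 4/100 = 4.0% (1.1-9.9) | 6/100 = 6.0% (2.2-12.6) |

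*Completers against treated and operated.* The largest shift is 15.8 - 11.1 = 4.7 points for r = 2. For r = 1 the treated and operated range is 4/37 to 5/37, or 10.8-13.5%; for r = 4 it is 4/40 to 8/40, or 10.0-20.0%. For r = 1 or 2 the shift is small next to interval widths of 22 to 25 points (24.8 - 2.9 = 21.9; 31.3 - 6.0 = 25.3).

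*Biopsied against treated and operated.* The events are the same, so the rate is multiplied by (36 + r)/B: 38/50 = 0.76 or 38/100 = 0.38. This factor does not depend on the assumed 4 events.

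*Biopsied against completers.* The direction is not fixed: 6/50 = 12.0% lies above 4/36 = 11.1%.

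**Changing the assumptions.** With 3 events among completers the rates are 3/36 = 8.3% for completers, 3/38 to 5/38 = 7.9-13.2% for treated and operated, and 3/50 to 5/50 = 6.0-10.0% for 50 biopsied. If the 2 early stoppers are not replaced, 34 completers with 4 events give 4/34 = 11.8%, against 4/36 to 6/36 = 11.1-16.7% for treated and operated. The pattern is the same.

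**The case against.** **The re-admission rate has a denominator.** A reader might infer from 12.4 alone that none exists. The documents do not support that: 12.4 calls it a safety measure and 12.2 defines the safety set. This stands. The defect is that the set fits the endpoint badly and 5.5.2 contradicts it.

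**Section 5.5.2 is about replacement.** A reader might infer that it removes patients from the safety analysis. It does not say so; it says who may be replaced, and 12.2 is the only text on who is included. This also stands, and 12.2 is probably the intended rule. But unevaluable for safety is still the phrase used, and it needs correcting.

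**Section 6.3 is probably loose wording for stopping study treatment.** That is plausible. A reader might infer that safety data on intolerant patients will be lost. The documents point the other way: the SAE windows are unconditional, and Section 4 assesses post-surgical complications in patients generally. Patients stopped under the infusion-reaction, lung or rash rules of 6.2.1 come off cetuximab only. What remains is an instruction that conflicts with other sections if followed literally.

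**The early stoppers may be few and their effect unknown.** This stands. Some will stop by choice, on the physician's decision or for progression (5.5.1), so it cannot be assumed that leaving them out flatters the rate.

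**Conclusion.** The point holds as a minor one, in two parts.

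First, the default safety set dilutes the only secondary endpoint relative to treated and operated patients, and 5.5.2 contradicts that set. In the assumed example the dilution multiplies the rate by 0.76 with 50 biopsied and 0.38 with 100. Leaving out two early stoppers moves the rate by at most 4.7 points, in an unknown direction. The numbers of re-admissions, early stoppers, replacements and biopsied patients are all assumptions; the documents give none of them. The dilution claim is limited to the comparison with treated and operated patients.

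Second, 6.3 conflicts with the SAE windows in 9.2 and 9.4 and with the protocol's own distinction between study and therapy. Those windows probably preserve most of the data, so who is counted matters more than what is collected.

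The endpoint is descriptive. The primary endpoint and the sample size of 36 are unaffected, because 12.2 and 5.5.2 agree on the two-dose and resection rule for efficacy. Section 6.3 does not conflict with 12.2.

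**What to change.** - **12.4:** state that the re-admission denominator is all patients who received any cetuximab, including a partial dose, and had surgery, whether or not they were replaced. Keep AE and SAE reporting for all biopsied participants, as 12.2 has it.
- **5.5.2:** delete the words 'safety and', so that the replacement rule concerns efficacy and correlative evaluability only.
- **6.3:** replace removal from the study with removal from protocol therapy, with safety follow-up through 28 days after surgery (9.2) and the one-month post-surgery visit. Both are needed, because that visit may fall up to two weeks before or after one month. The 3-day limit can stay.
- **5.5.1:** point to 6.2.1 and 6.3 for toxicity stops in place of 9.5.

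The cost is four short wording changes in one amendment. The one-month visit is standard of care and the SAE recording is already required. Limiting the 6.3 change to safety follow-up avoids adding research blood draws for these patients; full per-protocol follow-up could add them. The downside is that the reported complication rate may be slightly less favourable.
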